10.4.1 Informed consent

Individuals who agree to take part in the study will provide written consent at the baseline assessment visit. The researcher will first confirm understanding of what will be involved in taking part in the study and go through the consent form with the patient – including an explanation of why the researcher wishes to audio record the LEDs component of the assessment visit, confidentiality, the right to withdraw from the study and consent to be contacted by a second researcher for subsequent qualitative interviews. Any questions will be answered before written consent to participate is taken. Two copies of the consent form will be completed and signed by both the participant and the researcher taking consent (one for the participant and one for the research file). A photocopy of one of the original signed copies of the consent form will be made by the researcher and scanned by a member of the practice staff in to the medical records of the participant at the GP practice.

10.4.2 Baseline data collection and assignment of study number

Baseline data (see Section 16) will be collected by a mixture of participant self-report and researcher-led questioning. The researcher will register the participant on the study database. The database will allocate the participant a unique trial number and randomise them to intervention or control (see 11.3), if they are a patient from an individual randomisation practice. The unique trial number will be used on all of the participant's data collection forms. It is anticipated that baseline data collection will take approximately two hours and will be completed in one visit. Should the participant become tired and wish to complete baseline questionnaires on a second occasion, this visit should be completed within a week of the first assessment visit. All participants who consent to do so will have the LEDs component of the data collection audio-recorded. Audio recordings of

the LEDs component will be stored on universities (Liverpool, Plymouth, Swansea) managed network server, not on a computer's own hard drive.

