11.1 Individual level randomisation procedure

Following informed consent, a member of the research team (usually the RA) will access the password-protected randomisation website and enter the required participant details, including GP practice and participating GP's e-mail address, in order to obtain the participant's allocation. This allocation will not appear on the randomisation screen, thereby maintaining assessor blinding, but the randomisation procedure will trigger an automatic email to the identified member of the practice staff informing him/her of the participant's allocation. This email will identify the participant by his/her initials and unique trial number which the member of staff and GP can link to the participant's personal details when they access the web-based password protected study database. The member of the practice staff will retrieve participant's personal details and call them to arrange an appointment with a named GP at the practice. For trial management purposes, automatic emails (blinded, i.e. not including allocation) will also be sent to relevant team members e.g. Chief Investigator, trial manager, local PI as appropriate.

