12.1 Treatment as usual

Individuals randomised to TAU will receive GP care, a study-specific debt advice leaflet and RCPsych debt advice leaflet. TAU will begin with an initial consultation with a GP linked to the study. This initial GP assessment appointment should take place within a week of the participant being randomised. As with participants randomised to intervention arm, control arm participants will be contacted by a member of the practice staff to arrange an appointment with a named GP. The initial GP appointment will combine an assessment of both anxiety and depression, an assessment of need regarding medication and psychological therapy, and agreement regarding further treatment. This may include a referral to the local IAPT service and may normally include up to twelve further GP contacts. GPs may refer participants to IAPT services and other interventions as

[figure not shown]
they please and may arrange to review participants at ongoing appointments as required. The GP will provide each participant with a study-specific debt advice leaflet at the initial consultation.

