12.2 Intervention arm

Participants in the intervention arm will undergo a shared comprehensive assessment, starting with an initial GP review which mirrors that of the control group. At that visit, the GP will advise the participant of the intention to refer the participant to a CAB advisor and the GP will confirm that the participant is happy for this to be done. The GP will complete an electronic referral form that will include a statement that confirms the participant's agreement to be contacted by a CAB advisor and their consent to sharing of specified information between the CAB and GP, for the purposes of the shared comprehensive assessment. Participant's written, signed agreement to sharing of contact details and specific information for the purpose of the shared comprehensive assessment between GP and CAB will be retained by the GP practice. All participants will receive the study-specific debt advice leaflet and the RCPsych debt advice leaflet. Participants who do not wish to be contacted by a CAB advisor will be followed up as planned (see section 13), if they are still willing to do so. The GP will inform the study team via the web-based database that the participant has declined CAB intervention.

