18.1 Subject numbering

Each participant will be allocated a unique trial number generated by computer following consent and will be identified in all study-related documentation by their trial number. A record of names, addresses and telephone numbers linked to participants' trial numbers will be stored securely for administrative purposes on the study database.

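### In individually randomised practices the protocol ties randomisation to consent rather than to a completed baseline, so when baseline is split over two visits the later participant-reported measures can be recorded after the participant has learned the arm

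*Protocol*

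**What the plan says.** Protocol 10.4.2 covers the baseline visit. The researcher registers the participant and, in an individually randomised practice, "The database will allocate the participant a unique trial number and randomise them to intervention or control". The same section adds that "The unique trial number will be used on all of the participant's data collection forms". It expects baseline to take about two hours in one visit, with an exception counted from the initial visit: "Should the participant become tired and wish to complete baseline questionnaires on a second occasion, this visit should be completed within a week".

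Protocol 11.1 gives the procedure and names one precondition: "Following informed consent, a member of the research team (usually the RA) will access the password-protected randomisation website". Randomising sends the allocation automatically to practice staff, who telephone the participant to book a named GP. The researcher does not see the allocation. Protocol 18.1 also links the number to consent: "Each participant will be allocated a unique trial number generated by computer following consent".

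On what follows, 12.1 says: "This initial GP assessment appointment should take place within a week of the participant being randomised". In the intervention arm the opening GP review mirrors that of the control arm, and according to 12.2 it is there that "the GP will advise the participant of the intention to refer the participant to a CAB advisor".

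Three other places bear on the order. Section 7 has participants randomised after screening and consent. Section 10.4 places the BDI directly after consent, as both eligibility check and baseline value. Section 10.5, on posting the consent form to the practice, mentions the baseline visit before randomisation.

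**The concern.** Baseline values should be fixed before anyone who supplies them can know the allocation. Here the step that randomises is also the step that issues an identifier meant for every form, and its only stated condition is consent. A researcher could follow the text, register and randomise at the first visit, and collect the rest of the battery some days later.

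Many baseline measures rest on the participant's own answers, and participants cannot be masked to an offer of debt advice. Relief at being referred, or disappointment at not being referred, could colour those answers. Section 21.2 adjusts primary and secondary outcomes for baseline score, section 21.3 uses the CSRI for costs and the EQ-5D-5L for QALYs, and section 8.1.2 names hope, shame and rumination as possible mediators. A baseline that has already absorbed an early reaction to allocation would distort the adjusted difference on that scale, and further adjustment cannot repair it.

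**Working it through.** There is no figure in the plan to reproduce. The check is one of sequence, overlap and reach.

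**Sequence.** The stated conditions for randomising are:
- 10.4.2: registration by the researcher, with number and allocation produced together.
- 11.1: informed consent.
- 18.1 (number only): consent.
- 7 and 10.4: screening, including the BDI check.
- All other baseline measures: not named as a condition anywhere.

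The cross-reference for randomisation in 10.4.2 does not settle the matter. It points to 11.3 (Blinding), whereas the procedure is in 11.1.

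**Overlap.** Let day 0 be the first baseline visit, with randomisation that day.
- GP appointment: days 0 to 7 (12.1).
- Second baseline visit: days 0 to 7 (10.4.2).

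The windows coincide. Nothing prevents the GP appointment, where the referral is raised, from coming before the second baseline visit.

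**Which measures.** Table 1 lists 14 instruments at baseline: BDI-II, AUDIT, DAST, BAI, SWEMWBS, CSRI, EQ-5D, MANSA, Stanford Presenteeism Scale, the debt questionnaire, the hope scale, LED-S, OAS and RSQ.
- The BDI is completed straight after consent to decide eligibility, so it normally precedes randomisation. That leaves 14 − 1 = 13 that may be open.
- If the main trial is individually randomised, 21.2 minimises on depression severity, debt severity, employment and hopelessness. These must be known before allocation, so those items are protected in that phase. They are also the four pre-specified moderators.
- The minimisation text does not cover the pilot. There, debt severity, employment and hopelessness remain open in individually randomised practices.

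**How many participants the rule governs** (planned numbers from 11, 21.1 and 23, assuming all main-trial recruits follow the method chosen after the pilot):
- Pilot: 6 practices × about 10 = about 60 individually randomised, of 120.
- Individual main trial: total 2 × 195 = 390. Main phase 390 − 120 = 270. Individually randomised 270 + 60 = 330, and 330/390 = 85%.
- Cluster main trial: total 2 × 235 = 470. Individually randomised 60, and 60/470 = 13%.

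These counts show where the loose wording applies, not how many baselines would be affected. Only participants with a split baseline who are randomised at the first part, and who see the GP before the second part, are exposed. The protocol gives no figure for that fraction.

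**The case against.** The strongest reply is that the text leans towards baseline first. Section 10.4.2 describes data collection before registration, and 10.5 names the baseline visit before randomisation. Data are recorded on paper (18.2), so using the number on every form does not prove that it exists before the forms are filled in. One visit is expected. The practice's telephone call is made in both arms to book a GP, and nothing says that it discloses the arm. Several exceptions must therefore coincide. This stands as a limit on frequency. It does not close the gap, because 10.5 concerns the posting of a form and neither section deals with a split baseline.

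A reader might infer more than the documents support:
- **Randomisation before the BDI check.** Section 11.1 read alone mentions only consent. But section 7 puts screening before randomisation, and 10.4 ends the involvement of anyone scoring below 14.
- **Bias in the primary analysis.** The baseline BDI is the eligibility BDI, so the primary covariate is largely protected even when the visit is split.
- **Unmasked assessors.** Section 11.1 hides the allocation from the researcher, and 11.3 asks participants not to reveal the advice they received. What is at issue is the participant's knowledge.
- **The same defect and remedy in cluster practices.** Allocation there is fixed for the practice before the patient is recruited. Delaying the registration e-mail in 11.2 cannot place baseline before allocation.

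**Conclusion.** The point holds as a gap in the sequencing rule for individually randomised practices. Followed as written, the protocol permits participant-reported baselines other than the BDI to be recorded after the participant has learned the arm, when baseline is split. The measures at risk are mainly the secondary outcomes, the cost and EQ-5D-5L baselines, and the mediators. In the individually randomised part of the pilot (about 60 patients, whose data enter the final analysis) the moderators other than BDI severity are also at risk.

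No bias in points can be given, since neither the frequency of split baselines nor the size of any reaction to allocation is in the protocol. The affected fraction is probably small, because one visit is expected. The conclusion assumes that registration may take place at the first visit and that the participant learns the arm at the GP appointment. It is a cheap improvement worth making, not a threat to the primary comparison.

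**What to change.** Separate the two functions of the registration step. Issue the trial number at registration after consent. Enable randomisation, and with it the allocation e-mail, only once BDI eligibility is confirmed and every baseline form is marked complete, including those from any second visit. Reword 10.4.2 and 11.1 to state this order, and point the cross-reference in 10.4.2 to 11.1.

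The cost is a database setting and a few sentences. The downside is allocation up to about a week later for the few participants with a split baseline. Because 12.1 counts the GP appointment from randomisation, that interval moves with it. Follow-up is counted from the baseline visit (section 13), so for these participants slightly more of the follow-up period would precede the GP appointment, in both arms alike.

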10.5 Notification of new participant to GP practice

The study database will generate an e-mail to the local site manager and to a designated member of the GP practice staff notifying him/her of the participant's consent, unique study number and allocation. The member of staff will forward the e-mail to the appropriate study GP who will be able to login directly via a link in the e-mail to the web-based password protected study database to view participant details. A copy of the participant's consent form will be sent to the practice (usually by post) by a member of the research team, following the baseline assessment visit and randomisation (see section 11.1/11.2).

11 RANDOMISATION

In the internal pilot trial, relevant GP practice demographic information will be sent to CTU/study statistician by CRN in England, this activity will be supported by ABMU Health Board in Wales. Four practices (matched on their size and deprivation index score) in each of the three trial localities will be randomised to intervention or control arms and cluster (practice) or individual (patient) level allocation such that six practices are randomised to cluster allocation and six practices to individual allocation. To achieve total population research practice sites may be combined using a hub and spoke approach where available. The randomisation sequences and matching will be computer generated undertaken by an independent statistician working with the CTU. The CTU programming team will run checks before and during the trial to verify the integrity of the randomisation system.

Should the internal pilot show contamination to be a problem, for the main trial, the remaining practices will be randomised to intervention or control stratified by size and the deprivation (higher vs lower) of the populations they serve. If contamination is not found to be a problem, participants would be individually randomised to intervention or control.

Additional practices for the main trial will be identified and recruited once a decision has been made at the end of the internal pilot whether randomisation will be individual or cluster.

11.1 Individual level randomisation procedure

Following informed consent, a member of the research team (usually the RA) will access the password-protected randomisation website and enter the required participant details, including GP practice and participating GP's e-mail address, in order to obtain the participant's allocation. This allocation will not appear on the randomisation screen, thereby maintaining assessor blinding, but the randomisation procedure will trigger an automatic email to the identified member of the practice staff informing him/her of the participant's allocation. This email will identify the participant by his/her initials and unique trial number which the member of staff and GP can link to the participant's personal details when they access the web-based password protected study database. The member of the practice staff will retrieve participant's personal details and call them to arrange an appointment with a named GP at the practice. For trial management purposes, automatic emails (blinded, i.e. not including allocation) will also be sent to relevant team members e.g. Chief Investigator, trial manager, local PI as appropriate.

11.2 Cluster level randomisation procedure

During the internal pilot trial (and main trial if cluster randomisation continues), participants recruited at cluster randomised practices will be registered on the main trial database as soon as possible following written consent. A member of the research team (usually the RA) will access the

password-protected registration website and enter the required participant details, including GP practice and identified staff member e-mail address, in order to register the participant on the trial. This process will trigger an automatic email to the relevant member of the practice staff confirming the participant's consent and registration. The member of staff will forward the e-mail to the appropriate study GP. Both the member of staff and the study GP will access the web-based database to obtain the participant's personal details. For trial management purposes, automatic confirmatory emails (not including allocation) will also be sent to relevant team members e.g. Chief Investigator, trial manager, local PI as appropriate.

11.3 Blinding

Researchers conducting assessment interviews will not be informed of participant allocation and participants will be asked not to reveal to these assessors what type of debt advice they have received. At each data collection visit researchers will record which arm they believe participants are in, and record inadvertent unblinding.

To reduce contamination, wherever possible GPs will see either 'control' or 'intervention arm' patients only.

12 TRIAL INTERVENTIONS

Trial interventions are (i) GP treatment as usual (TAU) supplemented by debt management advice leaflets (control) or (ii) GP treatment as usual supplemented by debt management advice leaflets and primary care based CAB debt advice, including a shared GP/CAB Advisor comprehensive assessment (intervention). Following the initial GP appointment after randomisation, to enhance consistency, participants should continue to see this nominated GP or their named deputy where possible.

The trial intervention brings together two existing services:

- 1) Debt counselling provided by third sector providers e.g. the Citizens Advice Bureau
- 2) Primary care mental health services provided by general practices, supplemented by Improving Access to Psychological Therapies (IAPT) Services in England, and a variety of counselling and psychological therapies services in Wales.

This combined assessment will combine social, psychological, environmental, economic and medical perspectives in a formulation which will incorporate personal goals and a bio-psycho-social management plan. The intervention as a whole will incorporate four organisational mechanisms to optimise utility of the comprehensive assessment and the debt counselling (Figure 2).

12.1 Treatment as usual

Individuals randomised to TAU will receive GP care, a study-specific debt advice leaflet and RCPsych debt advice leaflet. TAU will begin with an initial consultation with a GP linked to the study. This initial GP assessment appointment should take place within a week of the participant being randomised. As with participants randomised to intervention arm, control arm participants will be contacted by a member of the practice staff to arrange an appointment with a named GP. The initial GP appointment will combine an assessment of both anxiety and depression, an assessment of need regarding medication and psychological therapy, and agreement regarding further treatment. This may include a referral to the local IAPT service and may normally include up to twelve further GP contacts. GPs may refer participants to IAPT services and other interventions as

[figure not shown]
they please and may arrange to review participants at ongoing appointments as required. The GP will provide each participant with a study-specific debt advice leaflet at the initial consultation.

12.2 Intervention arm

Participants in the intervention arm will undergo a shared comprehensive assessment, starting with an initial GP review which mirrors that of the control group. At that visit, the GP will advise the participant of the intention to refer the participant to a CAB advisor and the GP will confirm that the participant is happy for this to be done. The GP will complete an electronic referral form that will include a statement that confirms the participant's agreement to be contacted by a CAB advisor and their consent to sharing of specified information between the CAB and GP, for the purposes of the shared comprehensive assessment. Participant's written, signed agreement to sharing of contact details and specific information for the purpose of the shared comprehensive assessment between GP and CAB will be retained by the GP practice. All participants will receive the study-specific debt advice leaflet and the RCPsych debt advice leaflet. Participants who do not wish to be contacted by a CAB advisor will be followed up as planned (see section 13), if they are still willing to do so. The GP will inform the study team via the web-based database that the participant has declined CAB intervention.

Following the initial GP consultation and referral to CAB debt advice service, a CAB advisor will contact the participant to arrange an initial assessment appointment. Preferably this appointment will take place at the patient's own general practice to facilitate liaison between the two services. Wherever possible the first CAB assessment should take place within two weeks of GP referral. The primary aim of this initial CAB appointment will be to assess severity of debt, other social problems, individual's strengths and their key social and emotional goals. At the end of the assessment there will be an agreement as to whether the individual requires a higher level debt counselling intervention, or the basic debt counselling provision. The CAB intervention will be implemented utilising manuals, training and organisational agreements developed previously. Telephone liaison between the GP and CAB services may be required, along with occasional attendance at primary care meetings by a CAB advisor if appropriate. A shared comprehensive assessment sheet will be developed in the start-up phase of the study with GP, CAB and service user input. The assessment sheet will be a working document shared between the GP and CAB advisor - with participant consent. Participants will be able to have a printed copy of the completed assessment sheet should they wish to do so. CAB advisors will access the web-based password protected database to record study specific data.

Figure 2: Summary of trial interventions

